### 9.2 Level of Significance to be used

Determination of statistical significance for all analyses will be  $\alpha = 0.05$ . In the case of directional significance tests (e.g., tests using t-distributions), one-tailed tests will be used for *a-priori* directional hypotheses (Section 5.1) and two-tailed for non-directional hypotheses and *post-hoc* hypotheses).

### **9.3 Interim Analysis**

No interim analyses are planned.

### **9.4 Accounting for Missing, Unused, and Spurious Data**

Missing data will be identified as such in the database and will not be imputed or replaced for analytic purposes. Little's Missing Completely at Random (MCAR) test (Little, 1988) will be used to confirm that all missing data were missing "completely at random". Participants with small amounts of missing data ( $\leq 15\%$ ) will be excluded from analyses pairwise, whereas volunteers with large amounts of missing data ( $>15\%$ ) will be excluded listwise. Outliers are defined as individual scores that fall beyond an acceptable range (1.5 inter-quartile ranges above the third quartile or below the first quartile). Outliers will be identified as such in the database, and will not be included in data analyses, or will be transformed as appropriate for use in the data analytic strategy.

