#### 3.2 Target Population and Number of Volunteers

The target population for this study is adult male and female volunteers. The study requires up to 400 volunteers (200 completers) successfully complete the study to run statistical analyses. We anticipate up to 50% drop-out between study session 1 and 2 as attrition is high in MTurk populations (Mason and Suri, 2012). A “completer” is defined as completing the HBMT with at least 60% of the stems completed correctly and participating at both T1 and T2.

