## 9 STATISTICAL METHODS AND DATA ANALYSIS

### 9.1 Analyses for Main Study Hypotheses

Between group differences (comparing real vs. fake HBMT) in the change in state anger and state HAB across time points (change from time-point one to time-point two) will be primarily assessed with a mixed-designs ANOVA. Between group differences in state aggression measured at time-point two will be assessed with a General Linear Models (GLM) analysis controlling for trait anger and demographics (age and gender).

We will also plot effect of group comparing real vs. fake HBMT and time between time-points (24-96 hours) on change scores (time 2 anger/aggression minus time 1 anger aggression) and analyze this using a linear regression with an interaction term.

Lower order effects will be tested using corrected Fishers LSD, Tukey, Scheffe, or other pairwise test as appropriate. Appropriate data-transformations may be used as necessary to satisfy significance test requirements. Lower order effects will also be assessed with pairwise dependent means t-tests. Age and gender will be controlled as covariates. Mediation analyses (if used) will be performed using non-parametric Monte-Carlo bootstrapping procedures using PROCESS (see Hayes, 2017).

We may use age, gender, and trait measures as control variables in analyses.

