#### **10.6 Financial Incentives to Volunteers**

Volunteers will be paid up to \$5 for their participation in this study. All volunteers who complete time-point one of the study will receive \$3 and volunteers will receive an additional \$2 if they complete time-point two of the study. This rate is standard pay for MTurk work (See Hitlin, 2016). Most MTurk tasks pay 10 cents or less and result in less than an equivalent hourly wage of \$5. Volunteers will not be paid for participation in a time point if they do not complete an entire time point (i.e., progress through each activity/survey and reach the end screen; volunteers may skip any question they do not wish to answer on surveys without affecting payment). If a volunteer is terminated from the study as a result of website, server, or study program related failures (e.g., server goes down during study), they may request payment by contacting the PI directly. The PI will ask Volunteerscience.org to verify that the server/website failure had occurred and if so to pay the volunteer. The approval authority of such requests is the PI. Volunteerscience.com will track the performance of each volunteer using their MTurk handle and calculate compensation appropriately without sharing any PII (including MTurk handle) with ARL or WRAIR staff.

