**Your family doesn't take your education/career seriously.**

- |  | Very
Unlikely      | Unlikely              | Somewhat
Likely    | Likely                | Very
Likely        |
|--|-----------------------|-----------------------|-----------------------|-----------------------|-----------------------|
| 49. They just don't care about what's important to me.                                       |  |  |  |  |  |
| 50. I can't deal with it when they act this way.   |  |  |  |  |  |
| 51. I don't deserve to be treated this way. / They should just be quiet and leave me alone.  |  |  |  |  |  |
| 52. They can be so cruel/nasty/selfish sometimes.  |  |  |  |  |  |
| 53. People never understand me. / I always have to put up with things like this from people. |  |  |  |  |  |
| 54. I can't expect them to agree with everything I do or say.                                |  |  |  |  |  |

Scoring: Missattributin g Causation	Catastroph i Evaluating	Overgeneralizing	Demandingne ss	Inflammator y Labeling	Adaptiv e
1	2	3	5	6	4
7	8	12	9	11	10
16	14	13	18	17	15
21	22	23	20	19	24
28	25	27	26	29	30
33	34	35	36	31	32
41	40	38	39	37	42
45	43	44	47	46	48
49	50	53	51	52	54

Scoring instructions: Convert scaled responses to numbers as follows:

Very unlikely: 1

Unlikely: 2

Somewhat likely: 3

Likely: 4

Very likely: 5

Sum responses for each of the six subscales for overall score on each subscale. Item number legend for subscales provided in the table above.

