**Appendix F**

## State Aggression Questionnaire

Please indicate how often you have done each behavior during the past **24 hours**.

During the **PAST 24 HOURS**, how often have you:

Get angry with someone and yell or shout at them.

1 = Never      2 = One Time      3 = Two Times      4 = Three or Four Times      5 = Five or more times

Get angry with someone and kick or smash something, slam the door, punch the wall, etc.

1 = Never      2 = One Time      3 = Two Times      4 = Three or Four Times      5 = Five or more times

The following set of questions is asking about your **ONLINE BEHAVIOR OVER THE PAST 24 HOURS**.

I have removed or refused another person on a contact list for a chat, social network, or instant messaging program, without him/her doing anything and only for being who he/she was

1 = Never      2 = One Time      3 = Two Times      4 = Three or Four Times      5 = Five or more times

I have posted rude or unfriendly comments about someone on social networks.

1 = Never      2 = One Time      3 = Two Times      4 = Three or Four Times      5 = Five or more times

I have insulted someone using text messages or instant messaging programs (e.g., WhatsApp, SMS).

1 = Never      2 = One Time      3 = Two Times      4 = Three or Four Times      5 = Five or more times

I have made a false complaint about someone on a forum, social network, or online game.

1 = Never      2 = One Time      3 = Two Times      4 = Three or Four Times      5 = Five or more times

I have plotted with other people to ignore someone on social networks.

1 = Never      2 = One Time      3 = Two Times      4 = Three or Four Times      5 = Five or more times

I have posted or shared rumors or negative comments or negative news about someone on a social network

1 = Never      2 = One Time      3 = Two Times      4 = Three or Four Times      5 = Five or more times

\*I have “liked”, shared, or otherwise demonstrated support for negative content about another person online or on social media.

1 = Never      2 = One Time      3 = Two Times      4 = Three or Four Times      5 = Five or more times

The following questions are asking about your **DRIVING BEHAVIORS OVER THE PAST 24 HOURS**

Have you driven in the past 24 hours: Yes/No

I have called other drivers names aloud (e.g., “Jerk!”, “Idiot!”)

1 = Never      2 = One Time      3 = Two Times      4 = Three or Four Times      5 = Five or more times

I have made negative comments about other drivers

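### Survey items may be skipped, but Section 9.4 bars any replacement and no minimum-answered rule exists, so one blank can cost or distort a scale score or drop a returner from the adjusted aggression model

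*Combined protocol and SAP*

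**What the plan says.** - Section 10.6 (payment): "volunteers may skip any question they do not wish to answer on surveys without affecting payment".
- Section 9.4 (missing data): "Missing data will be identified as such in the database and will not be imputed or replaced for analytic purposes". Participants with at most 15% missing "will be excluded from analyses pairwise, whereas volunteers with large amounts of missing data", meaning above 15%, are removed listwise. What the 15% is a percentage of (scale, visit or whole record) is not said. Section 9.6 only points back to 9.4.
- Appendix B, scoring of the ACS, which is the measure of hostile attribution bias: "Sum responses for each of the six subscales for overall score on each subscale". Codes run from 1 to 5.
- Appendix F (aggression form): 21 frequency items coded 1 to 5, with 1 for never. By count, 2 are general, 7 concern online behaviour and 12 concern driving. The driving items follow the question "Have you driven in the past 24 hours: Yes/No". The appendix does not say how items are combined, how many must be answered, or what a non-driver does with the 12 driving items.
- Section 9.1: "Between group differences in state aggression measured at time-point two will be assessed with a General Linear Models (GLM) analysis", adjusted for trait anger, age and gender.
- Section 3.2 defines a completer as "completing the HBMT with at least 60% of the stems completed correctly and participating at both T1 and T2". Item completeness is not part of the definition.

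**The concern.** This point is about blanks inside returned forms, not about failure to return. The plan permits blanks by design, forbids filling them, and does not say how a scale with a blank is scored. Where the scoring rule is a sum, only two outcomes remain: the score is missing and the volunteer leaves every analysis that uses it, or the answered items are added and the blank acts as a zero. The first loses people who answered almost everything. The second records a skipped item as less hostile than the least hostile answer on offer.

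The 200 completers in Section 7.2 carry no allowance for such losses. For the aggression form, a primary outcome, the choice of scoring would be made after the data are in.

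**Working it through.** **The plan's own figure.** Inputs: d = 0.4, power 80%, 100 completers per arm (Section 7.2); alpha 0.05 (Section 9.2). A two-sided two-sample t-test needs 99.1 per arm, so 100 per arm and 200 in total, as stated. A one-sided test needs 78 per arm, 156 in total, which does not give 200. Power at 100 per arm is 80.4% two-sided and 88.0% one-sided.

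**ACS.** The scoring table gives each subscale 4 items in set A and 5 in set B. If four set A items are all at the lowest code, the sum is 4. With one of them blank, a raw sum is 3, below the possible minimum. If the score is instead set to missing, the volunteer is lost for that subscale. Change in a subscale uses 4 + 5 = 9 items, so with an independent skip probability q per item the share lost is 1 − (1 − q)^9:
- q = 0.5%: 4.4%
- q = 1%: 8.6%
- q = 2%: 16.6%

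**Aggression form.** One skip is 1/21 = 4.8% of the form and three are 3/21 = 14.3%, both inside the pairwise band if 15% is applied to this form. Four are 4/21 = 19.0%. If a complete total is required, one skip removes the volunteer from the aggression model. If answered items are added, the total falls by 1 to 5 points; someone answering never to the other 20 scores 20, below the minimum of 21.

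The skip rate q is not in the documents, so the range is assumed. Retained share = (1 − q)^21; n per arm = 100 × (1 − q)^21; power is from the noncentral t at d = 0.4.

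| q (assumed) | Returners lost | n per arm | Power, two-sided | Power, one-sided | Completers for 200 analysable |
|---|---|---|---|---|---|
| 0.1% | 2.1% | 97.9 | 79.5% | 87.4% | 205 |
| 0.5% | 10.0% | 90.0 | 76.1% | 84.8% | 223 |
| 1% | 19.0% | 81.0 | 71.6% | 81.3% | 247 |
| 2% | 34.6% | 65.4 | 62.2% | 73.6% | 306 |

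The last column is 200 / (1 − q)^21, rounded up.

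**Covariates.** A blank age or gender removes the volunteer from the adjusted model, because nothing may be replaced. So does a trait-anger score left missing by a blank on either of its two items (Appendix G). These losses are not in the table. Choosing the *prefer not to say* option for gender is a recorded answer, not a blank.

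**Non-drivers.** A non-driver who leaves the driving items empty lacks 12/21 = 57% of the form. By that denominator, this exceeds 15% and leads to listwise removal.

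**The case against.** A reader might infer that the plan necessarily removes, or scores too low, anyone who skips one of the 21 aggression items. The documents do not support that. The sum rule belongs to the ACS; Appendix F has no scoring rule, and a mean of answered items would avoid both outcomes. Such a mean amounts to filling the blank with the person's own average, so it sits awkwardly with the ban on replacement, but the text does not expressly exclude it.

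A reader might also infer that power on aggression falls below 80%. That rests on assumed skip rates, on independence and on a two-sided test. Section 9.2 makes tests of the directional hypotheses in 5.1 one-tailed where the test is directional, and Hypothesis 1 is directional. One-sided power stays above 80% up to 1% skips. Against this, the sample size reproduces only two-sided, and it is unclear whether 9.2 reaches the F-test of a GLM. Skips clustered in a few people would cost less, and the ACS directions ask for an answer to every thought, which may keep skips rare.

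Finally, it is tempting to say that aggressive respondents will skip the items that describe them. That is plausible but undocumented, and responses are anonymous. If it happened, averaging the answered items would share the bias.

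What stands is the ACS consequence, the covariate losses, and the absence of any scoring or minimum-answered rule for a primary outcome.

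**Conclusion.** The concern holds, conditionally for the aggression form. For the ACS, the written sum together with the ban on replacement leaves only a missing subscale or a blank counted as 0. For the aggression form, the same follows only if a complete total or a raw sum is chosen, and the plan leaves that choice open. Blank covariates remove returners from the adjusted model.

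The size cannot be fixed from the documents. Under independent skips of 0.5% to 2% and a complete-item requirement, 10% to 35% of returners leave the aggression analysis, with power of 76% down to 62% two-sided or 85% down to 74% one-sided. At 0.1% the loss is trivial. A definite fall below 80% power and selective skipping are not established. The change should still be made, because it is cheap and settles the scoring before data are seen.

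**What to change.** Replace the first sentence of Section 9.4, so that it does not contradict what follows, with:

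> Missing outcome scores are not imputed. Each scale or subscale is scored as the mean of its answered items if a stated minimum is answered: at least 85% of applicable aggression items, all but one item of each ACS subscale, and at least one of the two trait-anger items. For covariates only, missing age or trait anger is set to the sample mean, and blank gender is grouped with *prefer not to say* as its own category.

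Align the ACS scoring line in Appendix B with this. In Appendix F, state that the 12 driving items do not apply to volunteers who report no driving in the past 24 hours, and score driving as a separate subscale so that 9-item and 21-item means are not pooled. Say what the 15% in 9.4 is measured against, and that inapplicable items do not count towards it.

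Separate minimums are needed because 85% alone would fail the short scales: one skip leaves 3/4 = 75% or 4/5 = 80% of an ACS subscale and 1/2 = 50% of trait anger. The 85% is a new within-scale choice; the 15% in 9.4 applies to a participant's data.

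On the aggression form, 85% means 8 of 9 non-driving items and 11 of 12 driving items. Even at q = 2%, the share still lost is 1 − (0.98^9 + 9 × 0.02 × 0.98^8) = 1.3% for the first and 1 − (0.98^12 + 12 × 0.02 × 0.98^11) = 2.3% for the second, against 34.6% for a complete 21-item total.

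The cost is wording and a few scoring lines, with no change to conduct. With the form split, the plan must name which score carries the primary aggression test. The method assumes that a skipped item resembles the person's answered items, which does not fully remove bias if skipping is selective.

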#### 3.3 Study Design, Methodology, and Experimental Manipulations

The study consists of a two group design. Assignment to each of the two experimental conditions is determined randomly upon the volunteers’ arrival to the study webpage. However, the website will be programmed to achieve equal sample size across the two groups. The duration of participation for each volunteer is estimated to be about 60 minutes (total, including both time-points). Volunteers will complete the following as part of the study:

- a. HBMT: Volunteers will complete a computer-based hostile bias modification training where they are instructed to complete word fragments (words with missing letters) to form non-aggressive words. The word fragments are based on similar stimuli used in prior research on hostile bias (Anderson, Carnagey, & Eubanks, 2003; DeWall & Bushman, 2009). This task was validated in a previous study (WRAIR # 2574).
- b. Angry Cognitions Scale/HAB measure: This measure asks respondents to read hypothetical scenarios and indicate how they would interpret and respond to them. It was developed by Martin and Dahlen (2007) and will be used as a measure of HAB.
- c. Trait anger Scale: Brief measure of trait anger validated by Wilk et al., (2015).
- d. State Aggression Survey: This survey is adapted from several others in the literature to measure variance along the normal spectrum of aggressive behaviors in daily life that the average person might display (Álvarez-García, et al., 2016; Deffenbacher, et al., 2001; Deffenbacher, J. et al., 2002). The survey specifically asks about driving behaviors (e.g., yelling at other drivers), and public online behaviors (e.g., posting mean comments on social media), as well as generic public displays of aggression items (e.g., Gotten angry and slammed a door).

- e. State Emotion Survey: A short measure of state (current or recent) emotions over the preceding 24 hour period adapted from Goldberg et al., (2006) and Quartana and Burns (2007).
- f. Demographic questions: Volunteers will be asked to provide their age (whole number, not birth date), highest level of education, and gender. These will be used as statistical controls in analyses.

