### 7.2 Determination of Sample Size

200 volunteers (100 completers per condition) are needed to achieve statistical power of 80% and equal groups. The previous (and only other) study to test HBMT found a large effect of the real (vs. placebo) training on HAB ( $d = .78$ ), when HAB was assessed immediately after HBMT. However effect sizes are expected to be smaller in the present study as actual behavior is being assessed and there is a greater time delay (24-96 hours) between HBMT and the behavioral assessment. We will divide this effect size approximately in half ( $d = .4$ ) in our prediction for the second study. Given this effect size, a minimum of 200 completers who follow all task instructions will be needed to achieve 80% power.

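### Up to half the volunteers may have no time-point two outcome, and section 9.4 neither measures nor bounds the bias that arm-specific drop-out could cause; Little's test cannot confirm that the loss is harmless

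*Combined protocol and SAP*

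**What the plan says.** Section 3.2 of the combined protocol and SAP: "We anticipate up to 50% drop-out between study session 1 and 2 as attrition is high in MTurk populations". The same section sizes the trial on completers ("The study requires up to 400 volunteers (200 completers) successfully complete the study to run statistical analyses") and defines a completer by events after randomisation: "completing the HBMT with at least 60% of the stems completed correctly and participating at both T1 and T2".

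Section 9.4: "Missing data will be identified as such in the database and will not be imputed or replaced for analytic purposes". Little's test "will be used to confirm that all missing data were missing" completely at random. Volunteers with at most 15% missing are excluded pairwise, and those with more than 15% listwise. Nothing is said about what follows if the test rejects. Section 9.6, on who is analysed, only points back to 9.4.

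Section 8.8 places trait anger and state emotion before training, and Angry Cognitions Scale (ACS) set A and demographics after it. State aggression is collected at T2 only.

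Section 9.1 analyses state anger and hostile attribution bias by mixed-design ANOVA on change from time-point one (T1) to T2. T2 aggression is analysed by a general linear model adjusted for trait anger, age and gender.

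The documents contain no comparison of return rates by arm, no comparison of returners with non-returners, no weighting or likelihood-based method for the missing outcomes, and no sensitivity analysis.

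**The concern.** Randomisation makes the two arms comparable at T1. The comparison that answers Hypothesis 1 is made among those who come back one to four days later, possibly half of those randomised. Whether that subset is still comparable between arms is the main threat to the result, and the plan's only stated check is Little's test.

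That check cannot do what is asked of it. Not rejecting a null hypothesis does not confirm it. The test works on observed data, so it cannot rule out return that depends on T2 anger or aggression never recorded. The plan also does the same thing whichever way the test comes out. A selection effect could therefore be reported as a training effect, or hide one, without any planned analysis showing how fragile the conclusion is.

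**Working it through.** **1. The plan's own figures.** Inputs: d = .4 and 80% power (section 7.2), alpha = .05 (section 9.2). Two-sided normal formula: n per arm = 2(1.96 + .84)²/.4², which gives 99 after rounding up, or 198 in total. The exact two-sided t-test gives 99.08, so 100 per arm and 200 in total. Inflation for drop-out: 200/(1 − .5) = 400. Both stated figures reproduce, so the expected loss is covered for power.

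**2. Who is removed.** Counting the appendix items:

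- T1: trait anger 2 + state emotion 8 + ACS set A 24 + demographics 3 = 37.
- T2: ACS set B 30 + state emotion 8 + aggression questionnaire 22 (2 general, 7 online, 1 driving filter, 12 driving) = 60.

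A non-returner lacks at least 60/97 = 62% of items. That is well over 15%, so the listwise rule applies. The pairwise rule helps only volunteers who skip a few items.

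**3. Size of a possible bias.** Let m be the drop-out share in an arm and D the amount, in SD, by which drop-outs would have scored above returners. The full-arm mean is the returner mean + mD, so the returner mean is too low by mD. False benefit = m(real) × D(real) − m(fake) × D(fake). Every D here is an assumption; the documents give none. These are unadjusted T2 means.

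| Drop-out real / fake | D real / fake | False benefit (SD) |
|---|---|---|
| 50% / 50% | .4 / .4 | .20 − .20 = 0 |
| 50% / 50% | .4 / .2 | .20 − .10 = .10 |
| 50% / 50% | .4 / 0 | .20 − 0 = .20 |
| 55% / 45% | .4 / .2 | .22 − .09 = .13 |
| 30% / 30% | .4 / .2 | .12 − .06 = .06 |
| 30% / 30% | .4 / 0 | .12 − 0 = .12 |

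With 100 per arm the standard error is √(2/100) = .141 SD. Under a one-tailed .05 test with no true effect, a bias of .10 gives a false-positive rate of P(Z > 1.645 − .71), about 17%. A bias of .20 gives P(Z > 1.645 − 1.41), about 41%.

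Read the other way, an observed d of .4 is wiped out if real-arm drop-outs alone would have scored .4/.5 = .8 SD worse than returners, or .4/.3 = 1.33 SD at 30% drop-out.

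**4. What covariates and Little's test catch.** Simulation: 3,000 runs, 200 per arm, 50% returning in each arm, no true effect, one baseline covariate correlated .3 or .5 with the outcome. The log-odds of return change per SD of the T2 outcome as shown; these slopes are assumptions.

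| Slope, fake / real | Bias unadjusted | Bias adjusted | One-sided false positives, adjusted | Little's test rejects |
|---|---|---|---|---|
| 0 / 0 | about 0 | about 0 | about 5% | 5% |
| −.25 / −.25 | about 0 | about 0 | about 5% | 12–25% |
| 0 / −.5 | −.23 to −.24 | −.18 to −.21 | 44–47% | 13–22% |
| +.25 / −.25 | −.24 to −.25 | −.18 to −.23 | 45–51% | about 5% |

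The test rejects more often in the second row, where there is no bias, than in the fourth, where there is. It does not separate harmless loss from harmful loss.

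**5. What imputation adds.** Under the third row's selection, imputation that assumes missing at random and adds an ACS-like auxiliary (assumed correlations .3 to .6) left a bias of about −.15 to −.20. That is only some .01 to .05 SD better than covariate adjustment.

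**The case against.** The strongest reply is that the plan has some protection.

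- Section 9.4 is not purely complete-case, since partial responders are kept pairwise. This is true, but it does nothing for non-returners.
- Little's test can reject when return is related to observed T1 data. This is true, but no consequence follows.
- Adjusting aggression for trait anger, age and gender removes the bias if return depends only on those covariates and arm, and anger is analysed as change from T1. This stands. It is why bias is possible rather than certain.
- Section 9.4 never mentions drop-out, and section 10.6 lets volunteers skip items, so Little's test may have been meant for skipped items. On that reading non-return has no planned check at all.

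A reader might also infer that angrier volunteers will leave the real arm more often, because only that arm must withhold responses to some stems, and so that a positive result would be selection. The documents do not support this. Both arms have the same 12-second limit. The anticipated loss falls after training is finished and T1 has been paid, and the T2 session is the same for both arms. Different task instructions make arm-specific return conceivable, but no passage shows it. Likewise .20 SD is one end of an assumed range whose other end is 0, and 50% is an upper limit.

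**Conclusion.** The gap holds. The plan expects heavy loss of outcomes, excludes those volunteers by rule, bans imputation, and gives Little's test a role that it cannot fill and that has no consequence. It does not show that the result will be biased, in which direction, or by how much. Bias requires selection that differs by arm and remains after the planned adjustment.

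Under the stated assumptions, with 50% drop-out per arm, the unadjusted false benefit runs from 0 to .20 SD, at most half the planned d of .4, and shrinks with less drop-out. Confidence in the missing safeguard is high; confidence in any particular size or direction of bias is low.

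Nor should a reader infer that imputation or a mixed model alone would cure the problem. Both assume missing at random and leave most of the bias when return depends on unseen T2 values. Return rates by arm and the shift analysis carry the remedy.

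**What to change.** In sections 9.4 and 9.6:

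1. Delete the statement that Little's test confirms data are missing completely at random. At most, report it descriptively.
2. Report return rates by arm, and within arm by T1 trait anger and T1 state anger.
3. Remove the ban on imputation and add an analysis of all randomised volunteers with the pre-training T1 data, whether or not they reach the 60% stem threshold. Use a likelihood mixed model for anger and multiple imputation by arm for T2 aggression. Impute from trait anger and T1 state-emotion items, plus ACS set A and demographics where available; those two follow training, so volunteers who quit during T1 will lack them. ACS set A belongs in the imputation model and not among the outcome-model covariates, because it is measured after training. State that this analysis assumes missing at random and does not address drop-out that depends on unseen T2 values.
4. Add a shift (delta) sensitivity analysis in which the drop-out penalty varies separately by arm, including zero and equal shifts, and show the point at which the conclusion changes.
5. Report the completer analysis alongside.

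Cost: revised SAP text, some extra analysis and possibly wider intervals. No new data are collected and the sample size stays as it is.
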